- d A minimum of 24 hours is required between doses during sequential dosing weeks (eg, C1D1-C1D5; C2D1-C2D5). Infusions of BMS-986277 on Day 3 and Day 5 must be administered within 7 days of Day 1.
- e EOT visit is C26D29 ( $\pm$  7 days) or at the time of study treatment discontinuation. If within 7 days prior to FU Visit 1, the EOT visit may be skipped and FU Visit 1 should be completed and include all EOT biomarker samples.

**Table 2-5: On-Treatment Assessment Schedule (Monotherapy Expansion - BMS-986277 [Part 3 Cohort 3] Monotherapy with Option for Subsequent Nivolumab Therapy)(CA034001)**

Procedures a	Cycle 1 (28 days) b				Cycle 2 (28 days) b				Optional: Cycle 3 and each subsequent cycle (28 days; Nivolumab only) c			Notes		
	D1 d	D3 d and D5 d	D8 ( $\pm 3$ days)	D15 ( $\pm 3$ days)	D22 ( $\pm 3$ days)	D1 d ( $\pm 3$ days)	D3 d and D5 d	D8 ( $\pm 3$ days)	D15 ( $\pm 3$ days)	D22 ( $\pm 3$ days)	D1 ( $\pm 3$ days)		D15 ( $\pm 3$ days)	EOT e
	Safety	■	■	■	■	■	■	■	■	■	■		■	■
Targeted PE, Physical Measurements, Vital Signs, ECOG Performance Status	X	X	X	X	X	X	X	X	X	X	X	X	X	On each BMS-986277 dosing day, assessments (vital signs) will be performed at predose and every 15 minutes ( $\pm 5$ minutes) until 60 minutes following completion of infusion and then at 4 hours ( $\pm 30$ minutes) and 8 hours ( $\pm 1$ hour) postdose. See note in Table 2-1. On each nivolumab dosing day, vital signs will be performed at predose only.

**Table 2-5: On-Treatment Assessment Schedule (Monotherapy Expansion - BMS-986277 [Part 3 Cohort 3] Monotherapy with Option for Subsequent Nivolumab Therapy)(CA034001)**

Procedures a	Cycle 1 (28 days) b				Cycle 2 (28 days) b				Optional: Cycle 3 and each subsequent cycle (28 days; Nivolumab only) c			Notes		
	D1 d	D3 d and D5 d	D8 ( $\pm$ 3 days)	D15 ( $\pm$ 3 days)	D22 ( $\pm$ 3 days)	D1 d ( $\pm$ 3 days)	D3 d and D5 d	D8 ( $\pm$ 3 days)	D15 ( $\pm$ 3 days)	D22 ( $\pm$ 3 days)	D1 ( $\pm$ 3 days)		D15 ( $\pm$ 3 days)	EOT e

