### 5.1.5 Safety Follow-up

Participants will enter safety follow-up when the maximum treatment permitted per protocol has been administered (2 cycles of BMS-986277 for participants treated with BMS-986277 monotherapy [Part 1 and Part 3 Cohort 3] or 26 cycles of nivolumab for participants treated with BMS-986277 and nivolumab [Part 2 and Part 3 Cohorts 1-3]) or once the participant discontinues from study treatment (eg, at EOT).

During safety follow-up, all participants will be evaluated for any new and/or ongoing AEs for at least 60 days for participants treated with BMS-986277 monotherapy and 100 days for participants treated with BMS-986277 and nivolumab after the last dose of study treatment. All AEs considered related to study treatment must be followed to resolution, return to baseline or when deemed irreversible as indicated in [Sections 9.2](#) and [9.2.3](#). Although AE reporting is not required following the start of subsequent anti-cancer therapies, assessments at safety follow-up visits should continue and events considered related to study treatment reported. Note that participants treated with BMS-986277 monotherapy (Part 1 and Part 3 Cohort 3) will be required to attend safety follow-up visits 1 and 2. Participants treated with BMS-986277 and nivolumab (Part 2 and Part 3 Cohorts 1-3) will be required to attend all 3 safety follow-up visits.

Safety follow-up visit 1 (FU1) should occur 30 days from the last dose ( $\pm 7$  days) or may be performed on the date of discontinuation. Safety follow-up visit #2 (FU2) occurs approximately 60 days ( $\pm 7$  days) from last dose of study drug. Safety follow-up visit #3 (FU3) occurs approximately 100 days ( $\pm 7$  days) from last dose of study drug. Safety follow-up visits must be conducted in person.

During FU1 and FU2, participants will also be evaluated for viral shedding. If virus is detected during FU2, samples should continue to be collected at least every 30 days until virus is no longer detected.

All participants will be required to complete the safety follow-up visits as indicated in [Table 2-6](#) or [Table 2-7](#) regardless of whether or not they start new anti-cancer treatment, except those participants who withdraw consent for study participation.

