## 5) Age and Reproductive Status

- a) Males and Females, ages 18 or age of majority or older at the time of the informed consent
- b) Women of childbearing potential (WOCBP) must have a negative serum or urine pregnancy test (minimum sensitivity 25 IU/L or equivalent units of HCG) within 24 hours prior to the start of study treatment.
- c) Women must not be breastfeeding for the duration of study treatment and for 3 months following the last study treatment if treated with BMS-986277 monotherapy only or for 5 months following the last study treatment if treated with BMS-986277 and nivolumab.
- d) Participants treated with BMS-986277 monotherapy only: Women of childbearing potential (WOCBP) must agree to follow instructions for method(s) of contraception for the duration of study treatment with BMS-986277 and 3 months following the last study treatment.
- e) Participants treated with BMS-986277 and nivolumab: Women of childbearing potential (WOCBP) must agree to follow instructions for method(s) of contraception for the duration of study treatment with nivolumab and 5 months after the last dose of study treatment.
- f) Participants treated with BMS-986277 monotherapy only: Males who are sexually active with WOCBP must agree to follow instructions for method(s) of contraception ([Appendix 4](#)) for the duration of study treatment with BMS-986277 and 6 months following the last dose of study treatment. In addition, male participants must be willing to refrain from sperm donation during this time.
- g) Participants treated with BMS-986277 and nivolumab: Males who are sexually active with WOCBP must agree to follow instructions for method(s) of contraception ([Appendix 4](#)) for the duration of study treatment with nivolumab and 7 months after the last dose of study treatment. In addition, male participants must be willing to refrain from sperm donation during this time.
- h) WOCBP who are continuously not heterosexually active are also exempt from contraceptive requirements, and still must undergo pregnancy testing as described in this section.
- i) Due to the unknown risk of viral shedding in semen, all male participants (irrespective of the participant's vasectomy status or partner's pregnancy status) must agree to remain abstinent from penile intercourse or use a male condom during each episode of penile penetration during the treatment and until 6 months after the end of BMS-986277 treatment. Please see contraception requirements above in 5 f) and g).

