C4D15, C8D15, C12D15 f	predose	00:00			X	X			
Grade 3/4 hypersensitivity reaction			X	X	X	X			
EOT d			X	X	X	X	X	X	X
Follow up visit 1			X	X	X	X	X	X	X
Follow up visit 2 e			X	X	X	X	X	X	X

a EOI = End of Infusion, This sample should be taken immediately prior to stopping the infusion (preferably less than 2 minutes prior to the end of infusion). If the end of infusion is delayed to beyond the nominal infusion duration, the collection of this sample should also be delayed accordingly.

b Samples are relative to the start of nivolumab infusion on these days.

c Nivolumab ADA samples are only needed at C1D15 predose.

d EOT visit is at the time of study treatment discontinuation. If within 3 days of other visits, the EOT samples may be skipped.

e If virus is detected at the 60 Day Follow-up visit, samples should continue to be collected at least every 30 days until virus is no longer detected.

f Nivolumab PK and ADA samples will continue to be collected every 16 weeks (4 cycles) until end of treatment.

**Table 9.5-3: Pharmacokinetic (PK), Anti-Drug Antibody (ADA), and Shedding Sampling Schedule for Monotherapy Expansion - BMS-986277 (Part 3 Cohort 3) Monotherapy with Option for Subsequent Nivolumab Therapy (CA034001)**

Study Day of Sample Collection	Event	Time (Relative To Start of Infusion of BMS-986277 Dose ) Hour: Min	BMS-986277 Whole Blood PK Sample	BMS-986277 Serum ADA Sample	Nivolumab Serum PK Sample	Nivolumab Serum ADA Sample	BMS-986277 Shedding Sample (urine)	BMS-986277 Shedding Sample (saliva)	BMS-986277 Shedding Sample (stool) ( $\pm$ 7 days)
C1D1, C2D1	predose	00:00	X	X			X	X	X
C1D1, C2D1	EOI a	00:15	X						
C1D1, C1D5		01:00	X						
C1D1, C1D5		02:00	X						
C1D1, C1D5		03:00	X						
C1D1, C1D5		04:00	X						
C1D1, C1D5		08:00	X						
C1D3, C2D3	predose	00:00	X				X	X	X
C1D3, C2D3	EOI a	00:15	X						
C1D5	predose	00:00	X				X	X	X
C1D5	EOI a	00:15	X						
C1D8, C2D8		72:00	X				X	X	X
C1D15, C2D15		240:00	X	X			X	X	X
C1D22, C2D22		408:00	X	X			X	X	X
C2D5	predose	00:00	X				X	X	X
C2D5	EOI a	00:15	X						
C3D1 b	predose	00:00 f	X	X	X	X	X	X	X

**Table 9.5-3: Pharmacokinetic (PK), Anti-Drug Antibody (ADA), and Shedding Sampling Schedule for Monotherapy Expansion - BMS-986277 (Part 3 Cohort 3) Monotherapy with Option for Subsequent Nivolumab Therapy (CA034001)**

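### In combination participants the repeat-until-negative shedding rule is triggered only at a visit timed from the last nivolumab dose, so a positive last on-treatment sample may need no resample for up to 658 days

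*Protocol*

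**What the plan says.** Section 5.1.5 states the rule ("If virus is detected during FU2, samples should continue to be collected at least every 30 days until virus is no longer detected"). Footnote e to Table 9.5-2 repeats it ("If virus is detected at the 60 Day Follow-up visit, samples should continue to be collected at least every 30 days"), and footnote d to Table 9.5-3 does the same. In all three places the trigger is the 60-day follow-up visit.

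Section 5.1.5 also sets when that visit happens. Participants given both drugs enter safety follow-up after "26 cycles of nivolumab for participants treated with BMS-986277 and nivolumab", or earlier if they discontinue. Then "Safety follow-up visit 1 (FU1) should occur 30 days from the last dose"; "Safety follow-up visit #2 (FU2) occurs approximately 60 days", give or take 7 days, "from last dose of study drug. Safety follow-up visit #3 (FU3) occurs approximately 100 days".

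The dosing tables (7.1.4-1 and 7.1.5-1) give BMS-986277 on Days 1, 3 and 5 of Cycles 1 and 2 only, and nivolumab on Day 15 of each 28-day cycle for up to 26 cycles. In Tables 2-3 and 2-4, "EOT visit is C26D29" or the time of discontinuation.

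Table 9.5-2 takes urine, saliva and stool for shedding through C3D15, then again at EOT, FU1 and FU2. The rows at C4D15, C8D15, C12D15 and every fourth cycle after that are for nivolumab PK and ADA only. Table 9.5-3 (Cohort 3) has shedding sets at C3D1 and C4D1 for those who take nivolumab, then none until EOT.

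**The concern.** The rule is a safeguard: keep sampling until the virus is gone. It does that job in monotherapy, where the 60-day visit falls 60 days after the last infusion. Carried over to participants whose second drug continues for up to two years, the same words attach the trigger to the wrong event. A participant still shedding at the last on-treatment sample, the person the rule exists for, does not meet the trigger while on nivolumab, and the gap is longest for those who stay on treatment longest.

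For such a participant, persistence of a first-in-human oncolytic virus would go undocumented and time to clearance could not be estimated. Elsewhere the protocol does anchor virus-related follow-up to the virus: general-health follow-up (5.1.7.1) runs at least a year from the last BMS-986277 dose, and inclusion criterion 5i runs "until 6 months after the end of BMS-986277 treatment". This looks like an anchoring oversight, not a deliberate choice.

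**Working it through.** The documents state no length for the gap, so there is no figure to reproduce. It follows from the calendar.

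**Convention.** Study day = (cycle − 1) × 28 + day. Two stated figures confirm it. Section 8.1.1 puts a 7-day delay of Cycle 2 at Day 36, and C2D1 + 7 = 29 + 7 = 36. Table 9.5-2 lists C1D22 at 408 hours, and (22 − 5) × 24 = 408. Months use the SAP 9.1 factor of 30.4375 days.

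**Part 2 and Part 3 Cohorts 1-2, two virus cycles given, 26 nivolumab cycles completed**

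| Event | Study day | Days after last virus dose | Days after C3D15 |
|---|---|---|---|
| Last virus dose, C2D5 | 28 + 5 = 33 | 0 | – |
| Last on-treatment shedding set, C3D15 | 56 + 15 = 71 | 38 | 0 |
| Last nivolumab, C26D15 | 700 + 15 = 715 | 682 | 644 |
| EOT, C26D29 | 700 + 29 = 729 | 696 | 658 |
| FU1 | 715 + 30 = 745 | 712 | 674 |
| FU2 (only trigger) | 715 + 60 = 775 | 742 | 704 |

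- To EOT: 658 / 30.4375 = 21.6 months (21.4 to 21.9 over the ±7-day EOT window).
- If EOT is skipped because it falls within 7 days before FU1, as the tables permit: 674 / 30.4375 = 22.1 months.
- In Part 1, FU2 is nominally 60 days after the last virus dose; here it is 742.

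**Part 3 Cohort 3 with nivolumab.** C4D1 = 84 + 1 = Day 85, which is 85 − 33 = 52 days after the last virus dose. To EOT at C26D29: 729 − 85 = 644 days (21.2 months). Table 2-5 puts EOT at C26D29, but 26 nivolumab cycles starting at C3 would end in C28. On that count EOT is C28D29 = 756 + 29 = Day 785, and the gap is 700 days.

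**Earlier discontinuation (Part 2, Cohorts 1-2).** Days from C3D15 to FU1, with the EOT sample normally coming sooner:

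| Last nivolumab cycle | Last dose, day | FU1, day | Gap, days |
|---|---|---|---|
| 3 | 71 | 101 | 30 |
| 6 | 155 | 185 | 114 |
| 13 | 351 | 381 | 310 |
| 26 | 715 | 745 | 674 |

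**The anchor is an inference.** Section 5.1.5 does not name nivolumab in the FU2 timing. Three things support reading it that way: Section 7 lists nivolumab as study treatment; combination participants enter safety follow-up only after the nivolumab cycles or at discontinuation; and Table 2-7 times adverse-event collection from the last dose of any study drug.

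**The case against.** Several stronger readings are tempting, and the documents do not support them.

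- **Clearance is never documented.** Not so. Table 9.5-2 takes shedding sets at C2D7, C2D15, C2D22 and C3D15: 2, 10, 17 and 38 days after the last virus dose. A negative C3D15 result is evidence of clearance.
- **All 36 participants in Part 2 and 80 in Cohorts 1-2 are affected.** Those are the maximum numbers eligible. Someone is affected only if positive at the last on-treatment sample and then long on nivolumab. The documents give no rate for either.
- **Cohort 3 has the same exposure.** It is sampled 52 days after virus, close to a 60-day check. Only the repeat trigger is missing.
- **The barrier precaution lapses before anyone looks again.** Criterion 5i ends 6 months after the virus, but 5g and Appendix 4 run contraception or condom use to 7 months after the end of treatment for combination men with partners of childbearing potential, and Appendix 4 covers pregnant or breastfeeding partners. Semen is not a sampled matrix, so more sampling would not test that risk.
- **Monotherapy and combination shedding cannot be compared.** C2D15 and C2D22 are common to both, and Part 1 FU1 (30 ± 7 days) overlaps C3D15 (38 ± 3). Only the 60-day point is lost.

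Two objections limit certainty. Section 7.7, which holds the contact precautions, is redacted, as is text after the shedding section, and handling of positive results could sit there. The schedule-table footnotes also allow extra testing when clinically necessary. That is discretion, though, where 5.1.5 makes resampling a requirement after a positive FU2. Neither supplies the missing trigger in the visible text.

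**Conclusion.** The point stands in narrow form. On the visible text, a combination participant positive at the last on-treatment shedding sample who stays on nivolumab has no required resample until EOT. The upper bound is 658 days (21.6 months) in Part 2 and Cohorts 1-2 and about 644 days in Cohort 3, both for 26 completed cycles. Participants negative at that sample, or stopping early, are little affected.

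This rests on nominal visit days, two virus cycles, nivolumab counting as the last study drug for FU2, and nothing in the redacted text filling the gap. The number affected cannot be estimated from the documents. It is a defect in one trigger that is worth correcting, and does not show that the shedding schedule as a whole fails.

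**What to change.** In 5.1.5 and in the footnotes to Tables 9.5-2 and 9.5-3, tie the trigger to the end of BMS-986277 by applying the existing 30-day, until-undetected rule to any positive last on-treatment shedding sample, in addition to a positive FU2. Collect at the nivolumab visits already scheduled every 4 weeks. The nominal 28-day spacing satisfies the 30-day limit, but visit windows of ±3 days could stretch it to 28 + 3 + 3 = 34, so the footnote should allow for the window.

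Optionally, add one shedding set at the existing C4D15 visit in Part 2 and Cohorts 1-2. That is Day 84 + 15 = 99, or 66 days after the last virus dose, and gives a time point near the Part 1 60-day sample.

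Keep the C3D15, EOT, FU1 and FU2 sets. Moving C3D15 to Cycle 4 would leave nothing between day 17 and about day 66 after virus in Part 2 and Cohorts 1-2, and dropping the late sets would remove monitoring.

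Cost: a footnote amendment and extra urine, saliva and stool qPCR for participants still positive, plus one set per participant if C4D15 is added. No dose or treatment rule changes.

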### **5.1.6 Response Follow-up**

Participants with ongoing stable disease (SD), partial response (PR), or complete response (CR) at the EOT visit will enter the Response Follow-up period. This period will occur simultaneously with the safety, long-term general health status, and survival follow-up for the mentioned participants.

Participants will continue to have tumor assessments performed as outlined in [Table 2-6](#) or [Table 2-7](#) and [Section 9.1.1](#). Images should continue to be submitted to the imaging core lab during this period. Radiological tumor assessments for participants who have ongoing clinical benefit may continue to be collected after participants complete the survival phase of the study at the Sponsor's discretion.

### **5.1.7 Long-term Follow-up**

Long-term follow-up will include long-term general health status and survival follow-up. These assessments will be conducted in parallel to safety and response follow-up for the duration specified in the subsections below (see Sections 5.1.7.1 and 5.1.7.2).

#### **5.1.7.1 Long-Term General Health Status Follow-up**

After completion of the safety follow-up visits and in parallel to survival and response follow-up, all treated participants will enter long-term general health status follow-up. During either a visit or phone contact, general health status will be collected and must include specific assessment of new infections, malignancy, and serious adverse events that are hematologic, immunologic, or neurologic. Participation on other clinical trials and subsequent anti-cancer therapy (eg, chemotherapy exposure) will be collected as part of survival follow-up. Participants will be followed approximately every 3 months ( $\pm$  14 days) from the last required safety follow-up visit, for a minimum of 1 year from the last dose of BMS-986277 treatment.

#### **5.1.7.2 Survival Follow-up**

After completion of the safety follow-up visits and in parallel to long-term general health and response follow-up, all treated participants will enter survival follow-up. Participants will be followed approximately every 3 months ( $\pm$  14 days) from the last required safety follow-up visit, until death, loss to follow-up, withdrawal of consent, or conclusion of the study, whichever occurs first. The duration of survival follow-up is at least 3 years from the first dose of study treatment, although a longer follow-up period could be considered in selected cases if an efficacy signal is apparent. When contacted for survival by visit or phone contact, survival status and subsequent anti-cancer therapy including treatment on other clinical trials will be collected. BMS may request that survival data be collected on all treated participants outside of the 3 month specified window. At the time of this request, each participant will be contacted to determine their survival status unless the participant has withdrawn consent for all contact.

### **5.1.8 Data Monitoring Committee and Other External Committees**

BMS has developed a multi-layered process to ensure safety monitoring through close collaboration of study site investigators, the BMS study team, and the BMS Global Pharmacovigilance and Epidemiology (GPVE) led Medical Surveillance Team (MST). This

collaborative process constitutes the safety monitoring plan for the study. To support safety oversight, BMS has established ongoing processes for collection, review, analysis, and submission of individual adverse event reports and their aggregate analyses. Because this is an open-label study, GPVE, the BMS medical monitor (or designee), and the investigators will have access to all data necessary for safety evaluation.

BMS GPVE is an internal group that operates independently from the clinical team to monitor safety across all BMS protocols, and analyze all data in an unblinded fashion. Within BMS, an MST is established for investigational therapies under clinical development, and a member of GPVE chairs this team. In addition, signal detection is performed at least monthly and ad hoc throughout the study by the MST composed, at a minimum, of the GPVE medical safety assessment physician (Chairman of the MST) and GPVE single case review physician, the study Medical Monitor (or designee), the study biostatistician, and epidemiologist; all of whom, analyze the data in an unblinded fashion. Furthermore, the MST routinely monitors for actual or potential issues related to participant safety that could result in a change in the medical risk-benefit balance associated with the use of study treatment(s).

### **5.1.9 Blinded Independent Central Review**

Images will be submitted to an imaging core lab and may be reviewed by Blinded Independent Central Review (BICR) at any time during the study. See [Section 9.1.1](#) for further details.

## **5.2 Number of Participants**

- Part 1 (Monotherapy Dose Escalation - BMS-986277)
  - Initially, 3-6 participants per BMS-986277 monotherapy dose level, for a total of up to 24 participants. Additional participants (up to a total of 12) may be treated at any dose level to further evaluate the safety, PK, or pharmacodynamic profile. Therefore, the total sample size is up to 72.
- Part 2 (Combination Dose Escalation - BMS-986277 and nivolumab)
  - Initially, 3-6 participants per combination dose level. Additional participants (up to a total of 12) may be treated at any dose combination below or at the BLRM-RD for further evaluation of the safety, PK, or pharmacodynamic profile. Therefore, the total sample size is up to 36.
- Part 3 (Combination Expansion)
  - Cohorts 1-2 (BMS-986277 and nivolumab): Up to 40 evaluable participants per cohort. See [Section 10.1](#) for further details on sample size calculation.
  - Cohort 3 (BMS-986277 monotherapy with option for subsequent nivolumab therapy): Up to approximately 12 participants evaluable for pharmacodynamic endpoints will be treated in this cohort. See [Section 10.1](#) for further details on sample size.

## **5.3 End of Study Definition**

The start of the trial is defined as first visit for first participant screened. End of trial is defined as last visit or scheduled procedure shown in the Schedule of Activities for the last participant. Study completion is defined as the final date on which data for the primary endpoint was or is expected to be collected, if this is not the same.

[REDACTED]

